	6.1.1 ANALYSIS OF PRIMARY AND SECONDARY ENDPOINTS	
	6.2 SAMPLE SIZE AND POWER	
7	STUDY MEDICATION (STUDY DEVICE OR OTHER STUDY INTERVENTION)	
	7.1 DESCRIPTION	.13

8	SAF	ETY	MANAGEMENT	. 12
	8.1		IICAL ADVERSE EVENTS	
	8.2	Adv	erse Event Reporting	.12
9	STU		ADMINISTRATION	. 13
	9.1	DAT	A COLLECTION AND MANAGEMENT	.13
	9.2	CON	IFIDENTIALITY	.14
	9.3	Reg	ULATORY AND ETHICAL CONSIDERATIONS	.14
	9.3	3.1	Data and Safety Monitoring Plan	.14
	9 .3	3.2	Risk Assessment	.15
	9.3	3.3	Potential Benefits of Trial Participation	.15
	9 .3	3.4	Risk-Benefit Assessment	.15
	9.4	REC	RUITMENT STRATEGY	.16
	9.5	INFC	DRMED CONSENT/ASSENT AND HIPAA AUTHORIZATION	.16
	9.5	5.1	Waiver of Documentation of Consent/Assent and Alteration of HIPAA Authorization	.16
	9.6	Ραγι	MENT TO SUBJECTS/FAMILIES	.17
10) PL	JBLIC	ATION	. 17
11	RE	FERE	INCES	. 18

ABBREVIATIONS AND DEFINITIONS OF TERMS

AE	Adverse event
BMI	Body mass index
BMIZ	BMI Z score
CF	Cystic fibrosis
CFTR	Cystic fibrosis transmembrane conductance regulator
CHPS	Center for Human Phenomic Science
CYP	Cytochrome P450
FFMSEE	Fat free massSleeping energy expenditure
FMFFM	Fat massFat free mass
HAZFM	Height Z scoreFat mass
IvacaftorHAZ	Kalydeco, VX-770Height Z score
NDS Ivacaftor	Nutrition data systemKalydeco, VX-770
PHI NDS	Personal health informationNutrition data system
SAE PHI	Serious adverse eventPersonal health information
SEESAE	Sleeping energy expenditureSerious adverse event
ucOC%SEE	Undercarboxylated osteocalcinSleeping energy expenditure
WAZucOC%	Weight Z scoreUndercarboxylated osteocalcin
WAZ	Weight Z score

ABSTRACT

Context: Ivacaftor has been a novel FDA approved therapy for patients with CF and gating mutations who are 2 years and older. The FDA has recently approved Ivacaftor for use in children 6 months of age and above. Our Investigator Initiated Study is designed to evaluate the nutritional, growth and GI impact of ivacaftor treatment for this unique younger (6 months to 2 years) patient cohort and for whom FDA approval for treatment is now approved. This proposal directly extends our previous highly informative nutrition and weight gain investigation of ivacaftor treatment in the older patient cohort.

Objectives: The primary aims of the study are to evaluate the impact of 12 weeks of ivacaftor treatment in 6 month to 2 year old subjects with CF and gating mutations growth status and gut health and function in n=18 children with protocol evaluations at baseline (pre-treatment) and 6 and 12 weeks after clinically prescribed ivacaftor treatment has begun. Other outcomes of significant clinical interest in young patients with CF will be explored. All subjects will be evaluated at The Children's Hospital of Philadelphia, and will be recruited both regionally and nationally to ensure timely enrollment.

Study Design: Observational prospective study with evaluations before and after 12 weeks of ivacaftor treatment. An interim assessment at 6 weeks will also be included.

Setting/Participants: Eighteen subjects ages 6 months to 2 years of age cystic fibrosis and CFTR gating mutations who are in a general state of good health from cystic fibrosis centers in US and Canada.

Study Interventions and Measures: Subjects will be evaluated before and after ivacaftor treatment for sleeping energy expenditure, BMI Z score, gut health and function as indicated by plasma fatty acids, fecal elastase and fecal calprotectin. Dietary intake, growth status and velocity, and serum fat soluble vitamins, bile acids and calprotectin will also be assessed.

PROTOCOL SYNOPSIS

Study Title	Nutritional Impact of Ivacaftor Treatment in 6 month to 2 Year Old Children with CF Gating Mutations
Funder	Vertex Pharmaceutical and CHOP Center for Human Phenomic Science and Nutrition Center
Study Rationale	Cystic fibrosis (CF) is a genetic disease caused by mutations in the gene encoding the CF transmembrane conductance regulator (CFTR), a chloride channel in many types of cells. Most CF mutations either reduce the number of CFTR channels at the cell surface (synthesis and processing mutations) or impair channel function (gating or conductance mutations). Ivacaftor (Kalydeco®, Vertex Pharmaceuticals Inc.) was the first of a new class of drugs that improved CFTR gating dysfunction ¹⁻³ . For such mutations (G551D, G178R, S549N, S549R, G551S, G970R, G1244E, S1251N, S1255P, G1349D) that permit CFTR expression at the cell membrane but compromise its activity, ivacaftor increases the probability that the chloride channel is open and active. In randomized, double-blind, placebo controlled trials, ivacaftor treatment in individuals (ages 6 to adulthood) with at least one G551D mutation resulted in clinically significant improvements in weight and body mass index (BMI), pulmonary function, and patient reported quality of life outcomes (QOL) ^{3,4} . Lung function and weight changes occurred over eight weeks, then plateaued and were sustained over 48 weeks.
	In the initial trials ivacaftor treatment in individuals with at least one G551D mutation resulted in rapid and sustained weight gain, increased FEV ₁ %, decreased pulmonary exacerbations, decreased sweat chloride concentration reflective of increased CFTR activity, and improved patient reported health-related QOL outcomes ³⁻⁵ . Ivacaftor has shown similar benefit in younger children and has been approved for use in children 6 months of age and older. Ivacaftor was found to be safe and effective in 33 children in the KIWI study completed 24 weeks of treatment in the KIWI study, with significant reductions in sweat chloride concentration, and an average increase in weight Z score of 0.2±0.3 and BMI z score of 0.4 ± 0.4^6 . Some exocrine pancreatic function restoration was demonstrated in these young children, as Davies et al. ⁶
	In our recent longitudinal observational study of 23 subjects (ages 5 to 61 years), we identified several mechanisms for weight gain with 3-month ivacaftor treatment including decreased resting energy expenditure (REE), gut inflammation and dietary fat malabsorption, resulting in a positive energy balance and weight gain. Weight gain in this study was 2.5 kg and was associated with a significant decrease in REE percent predicted of 5.5%, and in fecal calprotectin of 30 ug/g stool, a measure of gut inflammation ⁷⁻⁹ .
	Several outcomes related to improved energy balance are considered in this proposal. Building on our results in older

	subjects, we will once again focus on the importance of determining the effect of ivacaftor treatment on clinically important non- pulmonary outcomes. Our primary aim in this study of young 6 month to 2 year old children is to determine if 12-week ivacaftor treatment results in decreased sleeping energy expenditure (REE) and improved growth status by BMI Z score. Our secondary aim is to determine improvement in gut health and function associated with fat digestion, including increased total plasma fatty acids and fecal elastase, and decreased fecal calprotectin. Exploratory aims include investigating the impact of ivacaftor treatment on dietary intake, length, weight and head circumference status and growth velocity, and on serum fat soluble vitamins, bile acids and calprotectin.
Study Objective(s)	We propose a longitudinal study design to determine whether 12 weeks of treatment with ivacaftor results in improvement in sleeping energy expenditure (SEE), growth status as BMI Z score, and gut health and function in n=18 children ages 6 months to 2 years with at least one CFTR gating mutation. We anticipate that these changes will accompany meaningful improvements in dietary intake, growth status and growth velocity, and serum fat soluble vitamins, bile acids and serum calprotectin in these young children.
	PRIMARY AIMS
	H1: Ivacaftor treatment will result in a significant reduction in SEE as percent predicted over 12 weeks compared to baseline, thereby increasing the energy available for weight gain and physical activity.
	H2: Ivacaftor treatment will result in significantly increased BMI Z score over 12 weeks compared to baseline.
	SECONDARY AIMS
	H3: Ivacaftor treatment will result in significantly improved gut health and function resulting in better dietary fat absorption as indicated by increased total plasma fatty acids and fecal elastase and decreased fecal calprotectin over 12 weeks compared to baseline.
	EXPLORATORY AIMS
	To determine the impact of ivacaftor treatment over 12 weeks compared to baseline in:
	 Dietary intake of calories and percent calories from fat Growth status for length, weight, head circumference and growth velocity Serum fat soluble vitamins A, D, E and K, bile acids, and serum calprotectin
Study Design	We propose a longitudinal study design to assess sleeping energy expenditure, improvement in BMI Z score, and improved gut health and function in n=18 children ages 6 months to 2 years with CF

	with a gating mutation (G551D, G178R, S549N, S549R, G551S, G970R, G1244E, S1251N, S1255P, G1349D) before treatment (baseline) and after 6 and 12 weeks treatment with ivacaftor.		
Inclusion and	Inclusion Criteria		
Exclusion:	 Cystic fibrosis with at least one CFTR gating mutation of these ten (G551D, G178R, S549N, S549R, G551S, G1244E, S1251N, S1255P, G1439D, or R117H) approved for treatment 		
	Age: 6 months to 2 years of age		
	 In their usual state of good health A clinical decision has been made for subject to begin ivacaftor treatment 		
	 Family committed to the 4 to 6 month study protocol with visits to CHOP that will last 2 or 3 days for the baseline visit (Visit 1) prior to ivacaftor and the 12 week visit (Visit 3) after clinically prescribed ivacaftor treatment has begun, and will last 2 days for the 6 week visit (Visit 2) after ivacaftor treatment has begun. 		
	 Note that ivacaftor is now approved by the FDA for 6 month to 2 year old children for the additional 28 CFTR mutations known to be responsive to ivacaftor potentiation, these will also be considered. With our limited samples size, the mutations that have shown the strongest improvement with treatment will be given priority for enrollment. 		
	Exclusion Criteria		
	 On parenteral nutrition Use of any inhibitors or inducers of cytochrome P450 (CYP) 3A 		
	 Liver function tests elevated above 3x the reference range for age and sex 		
	Other illness affecting growth or nutritional status Other contraindications described for inconfer thereasy		
	Other contraindications described for ivacaftor therapy		
Number Of Subjects	18		
Study Duration	Each subject's participation will last 4 to 6 months		
	The entire study is expected to last 15 months		
Study Phases	Screening: screening for eligibility and obtaining consent		
	Baseline: baseline study visit at CHOP		
	Follow up: 6 week visit at CHOP after confirmation of timing of the start of clinically prescribed ivacaftor treatment (±2 week window)		
	start of clinically prescribed lvacator treatment (± 2 week window) Follow up: 12 week visit at CHOP after confirmation of timing of the start of clinically prescribed ivacaftor treatment (± 2 week window)		
Safety Evaluations	As part of safety assessment, a serum comprehensive metabolic panel including the ALT and AST liver enzymes, complete blood		

	count and serum pre-albumin will be assessed (CHOP Clinical Laboratory).
	Dosing will likely be interrupted by the CF clinical care team in subjects with ALT or AST of greater than 5 times the upper limit of normal (ULN).
	Subjects will be asked about all adverse events at the 6 and 12 week protocol visits and during the bi-weekly phone calls, and rated by intensity (mild, moderate, severe). Serious adverse events will be reported as per various policies in a timely manner to CHOP IRB and CHPS.
Statistical And Analytic Plan	Primary Aims: The goals of the primary aims of this study are to determine whether ivacaftor treatment improves SEE and BMI Z score. Secondary Aims: The goal of the secondary aim is to determine whether ivacaftor improves gut health and function as measured by total plasma fatty acids, fecal elastase and fecal calprotectin (ug/g stool). Analysis of efficacy for the primary and secondary outcomes will be based on change from baseline (before treatment) in SEE% predicted (Schofield), BMI Z scores, total plasma fatty acids, fecal elastase and fecal calprotectin. The differences between baseline and 12 weeks continuous outcomes will initially be compared using paired-t-tests if continuous variables are normally distributed and nonparametric tests (Wilcoxon sign rank) if they are not. Subsequently, mixed effects longitudinal models will be performed to assess change over all three time points (baseline, 6 and 12 weeks), adjusting for potential covariates such as age, sex, and adherence to treatment. Chi-squared tests will be used for comparison of categorical variables before and after ivacaftor treatment. Using similar methods, exploratory analyses will examine improvement in dietary intake of calories and fat, in growth status (weight, length, and head circumference Z scores) and growth velocity (both absolute and Z scores), serum fat soluble vitamins, bile acids, and calprotectin.
DATA AND SAFETY MONITORING PLAN	Safety will be formerly monitored weekly by the study team. The study protocol will be carried out in accordance with OHRP guidelines and requirements. SAEs that are unanticipated, serious, and possibly related to the study intervention will be reported to the study sponsor, IRB, CHPS, and members of the research and clinical teams in accordance with requirements. Anticipated SAEs or those unrelated to the study intervention will be reported to the same individuals/entities in accordance with requirements. There will be ongoing collection of data on adverse events and compliance to the treatment protocol throughout the study by research staff and which will be summarized and reviewed monthly by the study Principal Investigator and the Study Team. Out of range non-clinically significant laboratory data will be reviewed continually by the PI and the study team.

Schedule of Study Procedures & Study Timeline

Table 1: Summary of Methods			
	Pre-treatment	Post ivacaf	tor treatmen
Assessment	Baseline	6 weeks	12 weeks
Energy Expenditure			
Sleeping Energy Expenditure (SEE)	\checkmark		
Diet - 3-day Weighed Food Record	\checkmark		
Fecal Elastase I (pancreatic function)	\checkmark		
Fecal and Serum Calprotectin (inflammation)	\checkmark		\checkmark
Biochemistry			
Serum Bile Acids	√		\checkmark
Plasma Fatty Acids			
CBC without differential	\checkmark		
Serum Pre-albumin	\checkmark		
Serum Retinol (Vitamin A)	~		
Serum α-tocopherol (Vitamin E)	\checkmark		
Serum 25(OH)D (Vitamin D)			
Serum undercarboxylated osteocalcin (Vitamin K)	\checkmark		
Anthropometry and Body Composition			
Adherence to lvacaftor,Enzymes, Medications	\checkmark	\checkmark	
Health History Questionnaire	\checkmark	\checkmark	\checkmark
Safety			
Serum Comprehensive Metabolic Panel (ALT, AST)	\checkmark		\checkmark
Adverse Events			

1 BACKGROUND INFORMATION AND RATIONALE

1.1 Introduction

Cystic fibrosis (CF) is a genetic disease caused by mutations in the gene encoding the CF transmembrane conductance regulator (CFTR), a chloride channel in many types of cells. Most CF mutations either reduce the number of CFTR channels at the cell surface (synthesis and processing mutations) or impair channel function (gating or conductance mutations). Ivacaftor (Kalydeco®, Vertex Pharmaceuticals Inc.) was the first of a new class of drugs that improved CFTR gating dysfunction¹⁻³. For such mutations (G551D, G178R, S549N, S549R, G551S, G970R, G1244E, S1251N, S1255P, G1349D) that permit CFTR expression at the cell membrane but compromise its activity, ivacaftor increases the probability that the chloride channel is open and active. In randomized, double-blind, placebo controlled trials, ivacaftor treatment in individuals (ages 6 to adulthood) with at least one G551D mutation resulted in clinically significant improvements in weight and body mass index (BMI), pulmonary function, and patient reported quality of life outcomes (QOL)^{3,4}. Lung function and weight changes occurred over eight weeks, then plateaued and were sustained over 48 weeks.

In the initial trials ivacaftor treatment in individuals with at least one G551D mutation resulted in rapid and sustained weight gain, increased FEV₁%, decreased pulmonary exacerbations, decreased sweat chloride concentration reflective of increased CFTR activity, and improved patient reported health-related QOL outcomes³⁻⁵. In the STRIVE study of 161 adolescents and adults (12+ years old), subjects gained 3.1 kg after 48 weeks of treatment compared to 0.4 kg for those on placebo³. In the ENVISION study of 52 younger growing children (6 to 11 years old)⁴, subjects gained 3.7 kg after 24 weeks of ivacaftor vs.1.8 kg for placebo. In both studies, weight gain and improved lung function occurred rapidly with a weight plateau by 16 weeks or earlier. In people with non-G551 gating mutations (KONNECTION study, 6+ years old)¹⁰, BMI Z scores improved 0.24 after eight weeks of treatment compared to -0.04 for placebo. A long term ivacaftor open-label phase that followed the STRIVE and ENVISION studies (PERSIST study)¹¹ as well as observational studies have shown persistence and stability of weight gain and improvement in nutritional status over two or more years^{12,13}.

Ivacaftor has shown similar benefit in younger children and has been approved for use in children 6 months and older.. Ivacaftor was found to be safe and effective in 33 children in the KIWI study completed 24 weeks of treatment in the KIWI study, with significant reductions in sweat chloride concentration, and an average increase in weight Z score of 0.2 ± 0.3 and BMI z score of 0.4 ± 0.4^6 . Some exocrine pancreatic function restoration was demonstrated in these young children, as Davies et al.⁶ noted an increase in fecal elastase concentrations in a small sample of children after 24 weeks ivacaftor treatment. Prior to treatment, 93% were PI with fecal elastase concentrations of <50 µg/g, and after treatment this increased 100 µg/g on average. Furthermore, in the KLIMB study, a long-term follow-up to the KIWI study, the increased fecal elastase concentrations were sustained with mean increase of 129 µg/g after 84 weeks of treatment¹⁴. These results suggest that exocrine pancreatic function early in life may be partially restored with ivacaftor^{6,15}.

In a recent open-label Phase 3 trial (the ARRIVAL study)^{16,17} in 18 children ages 1 to 2 years of age with CFTR gating mutations (G551D, G178R, S549N, S549R, G551S,

G1244E, S1251N, S1255P, G1439D, or R117H) who completed 24-weeks of treatment, ivacaftor was safe and effective in significantly reducing sweat chloride concentrations from 104.1 to 31.5 mmol/L, and improving (restoring) pancreatic function as indicated by increasing fecal elastase from 182 to 357 ug/g stool. Ivacaftor's impact on growth status or velocity for weight and BMI in these young children was not reported. Changes in energy expenditure with ivacaftor treatment in these young children has also not yet been explored. This current application will directly ddress gaps in knowledge related to the important non-pulmonary outcomes that are clinically very important in very young children.

In our recent longitudinal observational study of 23 subjects (ages 5 to 61 years), we identified several mechanisms for weight gain with 3-month ivacaftor treatment including decreased resting energy expenditure (REE), gut inflammation and dietary fat malabsorption, resulting in a positive energy balance and weight gain. Weight gain in this study was 2.5 kg and was associated with a significant decrease in REE percent predicted of 5.5%, and in fecal calprotectin of 30 ug/g stool, a measure of gut inflammation⁷⁻⁹. For the 16 subjects with PI, dietary fat absorption as measured by coefficient of fat absorption (CFA) improved 3%^{7,8,18}. Dietary fat intake increased significantly in all subjects⁷, and energy intake increased, particularly in those from Italy⁸. In subjects <20 years of age, improved weight and BMI status was accompanied by beneficial effects on muscle mass, muscle function and QOL. Improvement in pancreatic function (fecal elastase) was seen in 5 of 7 subjects with PS. Whether a similar improvement in REE, growth status and gut health and function related to improved fat absorption in young children with CFTR gating mutations is not known.

Several outcomes related to improved energy balance are considered in this proposal. Building on our results in older subjects, we will once again focus on the importance of determining the effect of ivacaftor treatment on clinically important non-pulmonary outcomes. Our primary aim in this study of young 6 month to 2 year old children is to determine if 12-week ivacaftor treatment results in decreased sleeping energy expenditure (REE) and improved growth status by BMI Z score. Our secondary aim is to determine improvement in gut health and function associated with fat digestion, including increased total plasma fatty acids and fecal elastase, and decreased fecal calprotectin. Exploratory aims include investigating the impact of ivacaftor treatment on dietary intake, length, weight and head circumference status and growth velocity, and on serum fat soluble vitamins, bile acids and calprotectin.

In addition to reduced dietary fat absorption, altered fatty acid metabolism has been shown in CF and Pl^{19,20}, and may be linked to CFTR dysfunction, and little is known of changes with CFTR modulator treatment. In the GOAL study, change in serum fatty acid concentrations with ivacaftor treatment were explored. Serum arachidonic acid levels decreased while linoleic and docosahexenoic acid levels did not change in 40 subjects with G551D CFTR mutation²¹. We previously demonstrated a significant increase in total plasma fatty acids from 8.5±1.6 to 10.2±3.6 mmol/L (P<0.01) with 3-month treatment of a fat-based nutritional supplement: linoleic, lauric, palmitoleic, oleic and docosatetraenoic acids all significantly increased as well¹⁹. We propose to assess a plasma fatty acid panel that includes concentrations for 22 individual fatty acids as well as total fatty acids, as an indicator of change in fat absorption.

Serum calprotectin is a marker for whole body inflammation including lung and gut inflammation in CF, and other chronic inflammatory diseases²²⁻²⁴, and will be assessed along with fecal calprotectin. Improvements in length, weight and head circumference status will likely result from an expected reduction in SEE in these children associated with

ivacaftor treatment. Furthermore, comparisons of metabolic profiles in children with CF and their healthy counterparts, showed that the children with CF had profiles indicating bile acid processing abnormalities²⁵. Whether ivacaftor treatment results in improved fatty acid profiles, gut and systemic inflammation (fecal and serum calprotectin), bile acids and fat soluble vitamin status as markers of improved fat absorption in young children with CFTR gating mutations is not known and represent novel and clinically meaningful outcomes in young children with CF.

We propose a longitudinal study design to determine whether 12 weeks of treatment with ivacaftor results in improvement in SEE, growth status as BMI Z score, and gut health and function in 18 children ages 6 months to 2 years with at least one CFTR gating mutation. There will be a mid-treatment evaluation at 6 weeks to explore the pace of the change in the primary and secondary outcomes. To plan the study, we assume that 1/3 of subjects will be recruited locally within a 150 mile radius of Philadelphia and the remaining 2/3 from other CF Centers in North America and will travel to Children's Hospital of Philadelphia (CHOP) for three protocol visits, each visit lasting 2 or 3 days, conducted at our Center for Human Phenomic Science (CHPS) and Nutrition and Growth Laboratory.

The primary aims of this study are to determine whether ivacaftor treatment reduces SEE and increases BMI Z score. Secondary aims are to determine if ivacaftor treatment improves gut health and function resulting in better fat absorption as indicated by increased total plasma fatty acids and fecal elastase, and decreased fecal calprotectin. Exploratory aims are to examine the impact on dietary intake, growth status and velocity, serum fat soluble vitamins, serum bile acids, and serum calprotectin as a measure of systemic inflammation.

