2.2 Secondary Aims

H3: Ivacaftor treatment will result in significantly improved gut health and function resulting in better dietary fat absorption as indicated by increased total plasma fatty acids and fecal elastase and decreased fecal calprotectin over 12 weeks compared to baseline.To determine if treatment with Ivacaftor results in increased dietary fat absorption using three methods:

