2.3 Exploratory Aims

- 1) To determine the impact of ivacaftor treatment over 12 weeks compared to baseline in:
 - a) Dietary intake of calories and percent calories from fat
 - b) Growth status for length, weight, head circumference and growth velocity
 - c) Serum fat soluble vitamins A, D, E and K, bile acids, and calprotectin

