5.1.2 Laboratory Evaluations

Plasma Total Fatty Acids: A total plasma fatty acid panel will be assessed (ARUP Laboratories) to measure change in status of 22 fatty acids.

Fat Soluble Vitamins: Serum vitamin A and vitamin E assessed at Craft Technologies Laboratories. Serum vitamin D determined using Liquid Chromatography-Tandem Mass Spectrometry (CHOP). As a measure of vitamin K status, % undercarboxylated osteocalcin ([name] Lab, Yale University) will be assessed.

Serum Bile Acids: Total serum bile acids and 14 bile acid concentrations will be assessed by liquid chromatography tandem mass spectrometry (ARUP Laboratories)

Serum Calprotectin: Serum calprotectin will be obtained as a marker of lung and gut inflammation^{22,23} using a Buhlmann MRP8/14 ELISA kit (Alpco, Salem, NH)).

Safety Assessment: As part of safety assessment, a comprehensive metabolic panel including the ALT and AST liver enzymes, complete blood count and serum pre-albumin will be assessed (CHOP Clinical Laboratory).

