Fecal Elastase I: Pancreatic function will be assessed at both visits by obtaining spot stool samples with fecal elastase 1 to determine the level of pancreatic enzyme activity^{32,33}. Subjects will be provided with the stool collection kit and proper instructions and supplies, and will bring a stool sample back the next day. The stool sample will be stored at -20°C, and analyzed with an enzyme-linked immunosorbent assay kit sent to ARUP Laboratory (Salt Lake City, UT).

Fecal Calprotectin: Spot stool samples will be obtained to determine fecal calprotectin, a marker for gut inflammation (CHOP Laboratories), determined using a QUANTA Lite® ELISA kit.

Dietary Intake: Three day weighed food record will be obtained and calories, macro- and micro-nutrient content averaged over the three days. Families will be trained by staff and provided with scales, spoons and all supplies necessary for the collection of the dietary data. Detailed verbal and written instructions will be provided to ensure that the recording procedures are clearly understood. Also assisting with this will come from the Center for Human Phenomic Science (CHPS) staff and Bionutrition Unit system^{34,35}. Dietary intake of all nutrients will be analyzed using Nutrition Data System for Research software version 2012 developed by the National Coordinating Center (NCC, University of Minnesota. Minneapolis, MN)³⁶.

Health Questionnaire: The questionnaire will be administered by interview by the research staff, and will consist of two sections. The Health History section has general questions about the subject's health history including documentation of medical history, recent hospital admissions and illnesses, medications, and nutrient supplement use. A section describes aspects of environment such household size, insurance for child and whether on

Medicaid. In addition to family contact information (name, address, phone numbers), contact information from two non-household contacts will be collected to maintain contact with the subject in the event that the family cannot be contacted at their primary residence.

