6.2 Sample Size and Power

Sample Size and Power: This is a longitudinal study of the effects of ivacaftor treatment on outcomes before and after 12-week treatment. The sample size of 16 subjects to complete the study has been determined as adequate to have the power to test the primary outcomes of decrease in SEE percent predicted value (7% change), an increase in BMI Z score of 0.3, and secondary outcomes of measures of gut health and function; an increase in plasma total fatty acids from 8.5 to 10.5 mmol/L, an increase in fecal elastase of 120 ug/g stool, and a decrease in fecal calprotectin (-30 ug/g stool change). Using STATA, power calculations were generated, with α =0.05, for paired data (n=16) within the same sample (before and after 12 weeks of treatment) using the changes described above for the primary outcomes and secondary outcomes.

Primary outcomes: A sample size of 16 subjects results in 86% power to see a decrease of 7% in **SEE** (i.e. from 115 to 108) with a standard deviation of the change of 9%, using a paired t-test two-sided significance level. We demonstrated a change of similar magnitude in REE in 24 subjects with CF gating mutation after 3-mo treatment with ivacaftor^{7,9}. For growth status, 16 subjects will provide 85% power to detect an increase in **BMI Z score** of 0.3 with a standard deviation of 0.4. In the KIWI study of 2 to 5 year old children with CFTR gating mutation treated with ivacaftor for 24 weeks, a BMIZ score increase of 0.4±0.4 was demonstrated⁶. We showed a BMI Z score increase over 12 weeks of 0.3±0.4 in our recent study of 18 children (5 to 19 years) with 12-week ivacaftor treatment⁷.

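### Fat-soluble vitamin status is offered as a marker of fat absorption, but the exploratory before-after test specifies no lipid, season or supplement term (minor)

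*Combined protocol and SAP*

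**What the plan says.** - **Interpretation.** The last paragraph on outcomes in section 1.1 lists "bile acids and fat soluble vitamin status as markers of improved fat absorption in young children with CFTR gating mutations" among the things not yet known, and calls these outcomes novel and clinically meaningful.
- **Formal status.** Section 2.3 makes "Serum fat soluble vitamins A, D, E and K, bile acids, and calprotectin" an exploratory aim, worded as impact of treatment. The hypothesis about absorption is H3 in section 2.2, which speaks of "better dietary fat absorption as indicated by increased total plasma fatty acids and fecal elastase and decreased fecal calprotectin". No vitamin is named there.
- **Analysis.** Section 6.1.1 and the synopsis (Statistical And Analytic Plan) apply methods similar to those for the main outcomes to "serum fat soluble vitamins, bile acids, and calprotectin". Those methods are a paired t-test or Wilcoxon test of change, then mixed models with age, sex and adherence given as examples of covariates.
- **Measures.** Section 5.1.2 states "Serum vitamin A and vitamin E assessed at Craft Technologies Laboratories", with no lipid ratio. Vitamin D is serum 25(OH)D. Vitamin K status is percent undercarboxylated osteocalcin.
- **Data at hand.** The 12-week draw (section 4.2.3) takes fatty acids and vitamins together, and section 4.2 calls the baseline and 12-week visits nearly identical. The 6-week draw has no vitamins. Exam dates are in the database (section 9.1). The health questionnaire (section 5.1.3) covers "recent hospital admissions and illnesses, medications, and nutrient supplement use", and enzyme use is assessed under Adherence.
- **Expected lipid change.** Section 6.2 plans for "an increase in plasma total fatty acids from 8.5 to 10.5 mmol/L".
- **Timing.** The synopsis states "The entire study is expected to last 15 months"; each child takes part for 4 to 6 months (section 3.2.1).

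**The concern.** With no control group, anything else that moves a vitamin level between Visit 1 and Visit 3 is counted as change on ivacaftor unless the analysis separates it. Three influences are obvious candidates.

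- Alpha-tocopherol is carried in plasma lipid, and the plan itself predicts a lipid rise.
- 25(OH)D varies with season, and the visits are months apart.
- Vitamin levels respond to supplements, and supplement use can change during follow-up.

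These dependencies are general physiology. The documents do not state them, so their size is assumed below. What is at stake is how a significant vitamin result may be read. Read as section 1.1 invites, a rise in raw vitamin E could be presented as a further sign of better absorption when it only restates the fatty acid result, and a rise in 25(OH)D could reflect the calendar.

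**Working it through.** **Inputs from the documents.** n=16 pairs, two-sided 0.05, fatty acids 8.5 to 10.5 mmol/L, SD 2.8 (section 6.2); 15 months in total (synopsis); 4 to 6 months per child (section 3.2.1).

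**1. The plan's own figure.** Section 6.2 states 80% power for fatty acids. The shift over SD is 2/2.8 = 0.714.
- Normal approximation: Φ(0.714 × √16 − 1.96) = Φ(0.897) = 81.5%, within 2 points of the stated figure.
- Exact noncentral paired t, 15 degrees of freedom: 76.1%.

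The SD is printed with a percent sign. Read as 2.8% of 8.5 it would be 0.238 mmol/L, a ratio of 8.4 and power near 100%, so 2.8 mmol/L is the workable reading. The exact t is used below.

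**2. Vitamin E.** The planned lipid rise is 10.5/8.5 − 1 = 23.5%. Its SD is 2.8/8.5 = 32.9% of baseline. Assume that vitamin E follows a fraction e of each child's relative lipid change, plus independent extra variation with SD s (as a fraction of baseline), and nothing else:

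shift = e × 0.235; SD = √[(e × 0.329)² + s²]; chance of significance from the noncentral t with noncentrality (shift/SD) × √16.

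| e | s | shift | SD | shift/SD | significant |
|---|---|---|---|---|---|
| 1 | 0 | 0.235 | 0.329 | 0.714 | 76% |
| 1 | 0.10 | 0.235 | 0.344 | 0.683 | 72% |
| 1 | 0.20 | 0.235 | 0.385 | 0.611 | 63% |
| 1 | 0.30 | 0.235 | 0.446 | 0.528 | 51% |
| 0.5 | 0 | 0.118 | 0.165 | 0.714 | 76% |
| 0.5 | 0.10 | 0.118 | 0.193 | 0.611 | 63% |
| 0.5 | 0.20 | 0.118 | 0.259 | 0.454 | 40% |
| 0.5 | 0.30 | 0.118 | 0.342 | 0.344 | 25% |

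At s=0 the vitamin E test is the fatty acid test under another name, so 76% is the ceiling for any e. At e=1 the expected rise equals the lipid rise, so there is no gain relative to lipid. At e=0.5 a simple ratio would fall, 1.118/1.235 = 0.905, or about −9.5%, even though nothing but lipid has acted. The ratio over-corrects when scaling is partial.

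**3. Season.** First visits can fall in 15 − 6 = 9 to 15 − 4 = 11 months. Assume a yearly sine wave of amplitude A, first visits spread evenly over W months, and d months between draws. The worst-case mean shift over start dates is

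2A × sin(πd/12) × |sin(πW/12)| / (πW/12).

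- W=9: the last factor is 0.300. d=3 gives 1.414 × 0.300 = 0.42A; d=6 gives 2 × 0.300 = 0.60A.
- W=11: the factor is 0.090. d=3 gives 0.13A; d=6 gives 0.18A.
- W=12: the factor is 0.

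With d at exactly 12 weeks (2.8 months) the values are 0.40A and 0.12A. In simulation (n=16, d of 2.8 or 4 months, A of 0.25 to 1 SD of change, worst start month), the false-positive rate is 6.5% to 27% for W=9 and about 5% to 7% for W=11.

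**4. Supplements.** No dose, or frequency of dose change, appears in the documents, so no size can be given.

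**The case against.** The strongest reply is that H3 already treats a lipid rise as a sign of better absorption. If lipid rises because absorption improved, a raw vitamin E rise agrees with the reading in section 1.1, and dividing by fatty acids removes part of the effect under study. This stands. The percentages above are conditional on no change relative to lipid. They are not false-positive rates for absorption, though a reader might take them so. It also rules out replacing the raw value by the ratio. It does not answer the narrower point that raw vitamin E adds little evidence beyond the fatty acid result.

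Other stronger readings are tempting but unsupported:

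- **A chance as high as 94%.** An SD of change of 25% of baseline with full scaling would give this, but section 6.2 implies about 33% for fatty acids, and extra independent variation can only add to that.
- **The plan rules out or ignores these factors.** The covariate list in section 6.1.1 is open, so the accurate statement is that none is specified.
- **Supplement dose is already held.** The documents record use; dose is not mentioned.
- **All four are raw serum levels that should rise.** Vitamin K status is a percentage marker, and improvement is a fall.
- **Season is a large bias.** For an 11-month window it is close to negligible.
- **Restricting to children with unchanged doses solves the supplement question.** That subset is chosen on a post-baseline variable that may itself respond to vitamin status.

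Finally, the aim is exploratory, has no power statement and lies outside H3, and section 1.1 frames the matter as an open question. This limits the severity.

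**Conclusion.** The point holds at minor severity. The plan offers vitamin status as a marker of absorption but specifies no term that would separate it from lipid level, season or supplement use.

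For vitamin E, a significant raw result is expected in about 51% to 76% of trials under full scaling and 25% to 76% under half scaling, with nothing acting but the lipid rise. This assumes that the planned 23.5% rise occurs, that the SD of 2.8 is in mmol/L, and the stated scaling and extra SD.

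For 25(OH)D, the worst-case mean seasonal shift is about 0.4 to 0.6 of the amplitude with 9 months of first visits and 0.13 to 0.18 with 11. The amplitude itself is unknown from the documents. The supplement limb is qualitative only.

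No primary or secondary conclusion is affected.

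**What to change.** 1. **Vitamin E.** Report alpha-tocopherol per total plasma fatty acids from the same visit beside the raw value, with neither replacing the other. Claim a vitamin E gain beyond the lipid rise only if the ratio also rises. A flat or falling ratio should not be read as evidence against better absorption. Total fatty acids are the only lipid measure listed, so label the ratio accordingly.
2. **25(OH)D.** Add a sensitivity analysis of the change that uses the seasonal difference between the Visit 1 and Visit 3 draw dates (the sine and cosine terms at Visit 3 minus those at Visit 1). Otherwise, label 25(OH)D descriptive.
3. **Supplements and wording.** Tabulate supplement and enzyme use at each visit, with dose only if it is recorded. Word the vitamin results as changes in status, not as evidence of absorption on their own.

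**Cost.** A few lines of analysis text and derived variables from data already planned; no extra blood or visits. The downsides are slightly more analysis, one or two extra parameters at n=16 with only two vitamin time points, and a more cautious conclusion.
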